10.7 CCI [REDACTED]

[figure not shown]
10.7.1 CCI [REDACTED]

CCI

[figure not shown]
10.7.2 CCI [REDACTED]

CCI

[figure not shown]

10.7.3

CCI

CCI

10.8 Appendix 8: Response Criteria

10.8.1 Lugano Classification (Cohorts A to D, and F)

Lugano Classification 2014 [Cheson, B. D., et al 2014].

This appendix describes the process for assessing treatment response according to the Lugano Classification [Cheson, B. D., et al 2014] (“Lugano” from now on) for malignant lymphoma. This assessment includes anatomic imaging with CT or MRI (size assessments of lymph nodes, extranodal lesions, spleen, and liver), metabolic imaging (whole body assessment with FDG-PET), and clinical findings (physical examination and bone marrow biopsy results), when these are available and appropriate.

Anatomic imaging may include CT, MRI or some combination of the 2, with details specified in the Site Imaging Manual. CT is the most common modality used, and for the purposes of this document the term “CT” will be used to represent all anatomic imaging, no matter which imaging modality is used.

Before treatment (“baseline”), on CT all focal lesions (nodal and extranodal) will be classified as “target” (selected for quantitative assessment) and “nontarget” (selected for qualitative assessment). The spleen will be assessed quantitatively (by measuring the vertical length), and the liver will be assessed qualitatively. The FDG-PET will be assessed using the 5-point scale (a method similar to the older Deauville criteria [Barrington, S. F., et al 2014]). If bone marrow biopsy is performed, or if there are any physical examination findings that cannot be evaluated by imaging, these should be documented.

After therapy has begun, response assessment will include anatomic response based on CT (when a CT is available), which includes target, nontarget, and new focal lesions, as well as spleen and liver size assessment. Metabolic response, when an FDG-PET is available, will be based on the 5-point scale along with qualitative assessment of changes in FDG uptake from preceding timepoints. Anatomic response, metabolic response, and clinical information will be combined to produce the overall response for each timepoint. The criteria are summarized in the table below, and detailed in the following sections.

Lugano Summary Table

The following tables summarize the assessments based on both CT and PET, as described in the summary table in the original publication [Cheson, B. D., et al 2014]. For details about implementation, please see the sections following the tables. LDi – Longest diameter, SDi – Short axis diameter, PPD – product of perpendicular diameters, SPD – sum of products of diameters.

Complete Response (CR)

CR	PET-Based Response – CMR	CT/MRI-Based Response - CR
Target lesions	Score 1, 2, or 3	Target nodes/nodal masses regress to <1.5 cm in LD _i ; no extranodal sites of disease remain
Nontarget lesions	Not applicable	Absent
Organ enlargement	Not applicable	Regress to normal
New lesions	None	None
Bone marrow	No evidence of FDG-avid disease in marrow	Normal by morphology; if indeterminate, negative by immunohistochemistry

CMR = complete metabolic response; CR = complete response; CT = computed tomography; FDG = 2-fluorodeoxyglucose; LD_i = longest diameter; MRI = magnetic resonance imaging; PET = positron emission tomography.

Partial Response (PR)

PR	PET-Based Response – PMR	CT/MRI-Based Response - PR
Target lesions	Score 4 or 5 without new lesions Reduced overall uptake (extent and/or intensity) compared with baseline	≥50% decrease from baseline in SPD of target lymph nodes and extranodal sites (up to 6)
Nontarget lesions	Not applicable	Anything other than progression
Organ enlargement	Not applicable	Spleen must have regressed by ≥50% in excess length
New lesions	None	None
Bone marrow	Residual uptake higher than uptake in normal marrow but reduced compared with baseline. If there are persistent focal changes in the marrow in the context of a nodal response and without recent growth factor use, perform biopsy, or consider MRI, or an interval scan.	Not applicable

CT = computed tomography; MRI = magnetic resonance imaging; PET = positron emission tomography; PMR = partial metabolic response; PR = partial response; SPD = sum of products of diameters.

Stable Disease (SD)

SD	PET- Based Response – SMD	CT/MRI-Based Response - SD
Target lesions	Score 4 or 5 (without new lesions)	<50% decrease from baseline in SPD of target lesions.
	No significant change in FDG uptake from baseline or nadir	No lesion shows progression
Nontarget lesions	Not applicable	No increase consistent with progression
Organ enlargement	Not applicable	No increase consistent with progression
New lesions	None	None
Bone marrow	No change from baseline	Not applicable

CT = computed tomography; FDG = 2-fluorodeoxyglucose; MRI = magnetic resonance imaging; PET = positron emission tomography; SD = stable disease; SMD = stable metabolic disease; SPD = sum of products of diameters.

Progressive Disease (PD)

PD	PET-Based Response – PMD	CT/MRI-Based Response - PD
Target lesions	Score 4 or 5 with an increase in overall uptake (extent and/or intensity) from baseline	Growth of any target lesion: Increase $\geq 50\%$ from nadir PPD and Increase in LDi or SDi from nadir of: ≥ 0.5 cm for lesions < 2 cm ≥ 1.0 cm for lesions ≥ 2 cm and Current LDi > 1.5 cm for a lymph node or ≥ 1.0 cm for an extranodal lesion
Nontarget lesions	Not applicable	Clear progression of preexisting nontarget lesions
New lesions	New FDG-avid foci consistent with lymphoma rather than another cause (eg, infection, inflammation). If uncertain regarding cause of new lesions, biopsy or interval scan may be considered	Regrowth of previously resolved lesions A new node > 1.5 cm in LDi A new extranodal site of any size, as long as its presence is unequivocal and attributable to lymphoma
Organ enlargement		When splenomegaly was already present, the excess length must increase by $> 50\%$ (≥ 1 cm absolute increase) from nadir. If no prior splenomegaly, or prior splenomegaly had resolved, spleen length must increase by ≥ 2 cm to > 13 cm.

PD	PET-Based Response – PMD	CT/MRI-Based Response - PD
Bone marrow	New or recurrent FDG-avid foci, confirmed by biopsy	New or recurrent involvement

CT = computed tomography; FDG = 2-fluorodeoxyglucose; LDi = longest diameter; MRI = magnetic resonance imaging; PET = positron emission tomography; PD = progressive disease; PMD = progressive metabolic disease; PPD = product of perpendicular diameters; SDi = short axis diameter.

Anatomic Disease Assessment

Anatomic assessment specifically refers to the size of focal lesions or organs, assessed using computed tomography or magnetic resonance imaging. As stated previously, for simplicity the term “CT” will be used to represent all anatomic imaging.

Screening (Baseline) Assessment

Documentation of focal lesions

All focal lesions caused by lymphoma are identified at baseline and classified as measurable or nonmeasurable. Up to 6 of the measurable lesions are selected to serve as “target” lesions, which are then followed quantitatively throughout the study. All other focal lesions are documented as “nontarget” lesions, and evaluated qualitatively thereafter.

Measurable and nonmeasurable lesions

Malignant lymph nodes (nodal lesions) are considered measurable if they are consistent with lymphoma, clearly and reproducibly measurable in 2 dimensions on an axial slice, and measure >1.5 cm in LDi when assessed by CT/MRI scan, irrespective of scanner type and slice thickness/interval. Extranodal lesions are considered measurable if they are consistent with lymphoma, clearly and reproducibly measurable in 2 dimensions on an axial slice, and are ≥1.0 cm in both LDi and SDi when assessed by CT/MRI scan, regardless of slice thickness. In lymphomas that are FDG-avid, a lesion must be PET-positive (show FDG uptake greater than the surrounding tissue) to be measurable.

Lesions considered nonmeasurable include:

- Lymph nodes and nodal masses that are PET-positive and considered consistent with lymphoma, but that do not meet the size and reproducibility requirements to be considered measurable, and lesions visible on PET but not CT
- PET-negative lesions which meet the size criteria for measurability, and are considered consistent with lymphoma, in lymphoma that shows FDG avidity in other lesions
- Uni-dimensionally measurable lesions (clearly measurable in only one dimension)
- Extranodal lesions which do not meet the requirements for measurability, but are considered to be clearly due to lymphoma

- Truly nonmeasurable/assessable sites of disease, including:
 - Effusions and ascites
 - Bone lesions
 - Brain lesions, CNS lesions, leptomeningeal disease
 - Mucosal lesions in the gastrointestinal tract
 - Pleural, peritoneal or bowel wall thickening

Target and Nontarget Lesions

Up to up to 6 target lesions will be selected from among the measurable lesions and documented as target nodal and target extranodal lesions. Target lesions should be selected based on their size (largest lesions preferred) and suitability for reproducible measurements. Measurements of the LDi and SDi should be made in the axial plane on the slice of the tumor with the longest in-plane diameter. Calculate the PPD for each target lesion and the SPD for all target lesions.

Nontarget lesions will be all focal (nodal and extranodal) lesions that are consistent with lymphoma, but not chosen as target lesions, whether they were measurable or not.

Once lesions are designated as target or nontarget, those designations may not change during later assessments.

Spleen Assessment at Baseline

Splenic involvement will be assessed quantitatively, as a separate category from the assessment of measurable or nonmeasurable focal lesions. The spleen length will be measured from cranial to caudal. All spleen measurements referred to hereafter will refer to this cranio-caudal measurement. The spleen is considered normal if it is less than 13 cm, or if the spleen has been removed surgically. It is considered enlarged if it is greater than 13 cm in length. The portion of the measurement that exceeds 13 cm will be considered the abnormal portion.

Liver Assessment at Baseline

Hepatic involvement will be assessed qualitatively, separately from the assessment of measurable or nonmeasurable disease. At baseline, the liver will be assessed qualitatively as either normal or enlarged, and should only be documented as enlarged if there is clear evidence (based on biopsy or imaging) that the enlargement is due to lymphoma, and not to benign causes.

Anatomic Response (CT-based postbaseline assessment)

Target lesions

At every timepoint after screening, each target lesion is measured. Calculate the PPD for each target lesion and the SPD for all target lesions together. Response categories are as defined below:

- Complete Response: All target lymph nodes must have regressed to normal size defined as ≤ 1.5 cm in LDi. Target extranodal sites must be absent (0 by 0 cm).
- Partial Response: $\geq 50\%$ decrease in SPD of target lesions from baseline, and no individual lesion meets the criteria for progression.
- Progressive Disease: Target lesion progression is based on the progression of any single lesion (not a change in the SPD), which meets all of the following requirements:
 - The lesion must have increased by $\geq 50\%$ from its nadir in PPD.
 - For a lymph node, it must be > 1.5 cm in LDi, and for an extranodal lesion it must be ≥ 1.0 cm in LDi.
 - And one of the following:
 - For lesions < 2 cm at nadir, the lesion's LDi or SDi must have increased by ≥ 0.5 cm at the current timepoint from its nadir.
 - For lesions ≥ 2 cm at nadir, the lesion's LDi or SDi must have increased by ≥ 1 cm at the current timepoint from its nadir.
- Stable Disease: A target lesion assessment of SD requires all of the following:
 - Target lesions do not meet the criteria for CR or PR
 - No individual lesion meets the criteria for progression
- Not Evaluable: When a target lesion identified at baseline cannot be evaluated at a postbaseline timepoint due to missing imaging, poor image quality, changes in the lesion or background that precludes assessment, or focal therapy or other procedures that change the lesion size, the target lesion assessment will be NE, unless progression is assessed in another target lesion.

Nontarget lesions

Nontarget lesions will be assessed at each post baseline timepoint individually and as a group. Response categories are as defined below:

- Absent/Normalized (CR): All individual nontarget nodal lesions must have returned to normal size. All extranodal lesions must have disappeared.
- Unequivocal Progression (PD): Any individual nontarget lesion must unequivocally progress in the context of the overall disease burden to be assessed as PD. For increased thickening of the wall of a hollow viscus, the reviewer will use their cautious judgment to determine whether the increase is most likely caused by disease progression.

- PD should not be called based on enlarging pleural effusions or ascites, or enlarging lytic bone lesions, and rather, the overall assessment should be based on the rest of the disease burden.
- Stable Disease: At least one nontarget lesion is still present, or a node enlarged, without any individual lesions showing unequivocal progression.
- Not Evaluable: When an individual nontarget lesion lymph node, extranodal lesion, or nonmeasurable disease cannot be assessed at a postbaseline timepoint due to missing imaging, poor image quality, changes in the lesion or background that precludes assessment, or focal therapy to a lesion, the individual nontarget lesion will be assessed as NE. The assessment of the nontarget lesions as a whole will be NE if any of the nontarget lesions are NE and none are PD.

New lesions

Lesions will be considered new if they were not present at the baseline timepoint but are visible at the current timepoint.

A node consistent with lymphoma will be recorded as a new lesion if it was previously normal in size and is now >1.5 cm in LD_i. An unequivocal, new extranodal lesion consistent with lymphoma of any size is considered a new lesion. If multiple new extranodal lesions are noted, at least one should be recorded as a new lesion.

New lesions must be consistent with lymphoma rather than another etiology (eg, infection, inflammation) and must be PET-positive, if PET is available. New lesions will be treated as PET-positive when PET is not available to confirm avidity.

Some types of truly nonmeasurable lesions generally require further verification that they are attributable to lymphoma through biopsy or cytology. These include ascites, pleural or pericardial effusions, and lytic bone lesions. They may be recorded as new lesions only when there is other evidence of progression.

Other truly nonmeasurable lesions will not require verification to be considered a new lesion, as long as their appearance is unequivocal in the judgment of the reviewer:

- Nonmeasurable lesions such as brain and CNS lesions including leptomeningeal disease attributable to lymphoma
- Nonmeasurable nodal masses such as infiltrative mesenteric masses or retroperitoneal masses

Extranodal lesions which disappeared and then reappeared at a later timepoint will have the same effect as a new lesion, but are not designated “new”.

Spleen response

The spleen will be measured in the craniocaudal length as at baseline, and the enlarged portion calculated by subtracting 13 cm. Response categories for the spleen are as defined below:

- Normal (CR): Spleen was enlarged at baseline and has regressed to ≤ 13 cm at the current timepoint or the spleen was assessed as normal at baseline and is still normal, or there is radiological evidence of splenectomy at baseline.
- Partial Response (PR): Spleen was assessed as enlarged at baseline, and its excess length has decreased by $\geq 50\%$.
- Stable Splenomegaly (SD): No decrease consistent with PR and no increase consistent with progression.
- Unequivocal increase (PD): The spleen is assessed as PD if any of the following are true:
 - Recurrent splenomegaly: A spleen which was abnormal at baseline (> 13 cm) first returned to normal, but at the current timepoint the spleen increases by > 2 cm from its nadir and the length is > 13 cm.
 - New splenomegaly: No prior splenomegaly and spleen increases by > 2 cm from baseline and the length is > 13 cm.
 - Progression of existing splenomegaly: A spleen which is abnormal at baseline has the enlarged portion increase by $> 50\%$, and by ≥ 1 cm in absolute measurement, at the current timepoint from its nadir value.

Liver response

The liver will be assessed qualitatively. Response categories are as defined below:

- Normal (CR): Liver was assessed as enlarged at baseline and has regressed to a normal size or still enlarged but without evidence of lymphoma involvement, OR the liver was assessed as normal at baseline and continues to be normal.
- Stable Disease (SD): Liver is considered stable if there is persistent liver involvement with evidence based on imaging (CT or MRI) or biopsy that there is infiltration by lymphoma of the entire organ.
- Unequivocal increase (PD): New hepatomegaly, recurrent hepatomegaly, or definite growth from prior liver size, and there is evidence that this is due to lymphoma infiltration.

Anatomic Response

The anatomic response should be assessed at each postbaseline timepoint based on the criteria below. Liver size alone should never be the basis for response determination by itself, but only support the assessment as supplemental information.

Target	Nontarget	Spleen	New Lesions	Anatomic Response
CR	CR	CR	No	CR*
CR	CR	PR	No	PR**
CR	SD	CR	No	PR**
PR	CR/SD	CR/PR	No	PR
PR	CR/SD	SD	No	SD
SD	CR/SD	CR/PR	No	SD
SD	CR/SD	CR/PR/SD	No	SD
Any non-PD	NE	CR/PR/SD	No	NE
NE	Any non-PD	CR/PR/SD	No	NE
PD	Any	Any	Any	PD
Any	PD	Any	Any	PD
Any	Any	PD	Any	PD
Any	Any	Any	Yes	PD

CR = complete response; NE = not evaluable; PD = progressive disease; PR = partial response; SD = stable disease.
 *if the liver shows lymphoma involvement, it must resolve to allow CR
 **Spleen can drive PR on its own if no target lesions were identified at baseline

Metabolic Response

In addition to anatomic imaging, metabolic imaging using FDG-PET can contribute to the assessment, if it is available, or may form the sole basis for response if no anatomic imaging is performed at a time point. An FDG-PET is required at screening. Subsequent time points that require PET are shown in the schedule of assessments. If lesions are not FDG-avid at baseline, PET is not required at follow-up timepoints unless clinically indicated.

PET Assessment

For every FDG-PET scan, a 5-point scale score is obtained by comparing the SUVmax of the lesion that shows the greatest tracer uptake (the “hottest” lesion) to surrounding normal tissue, to a region of interest (ROI) placed over blood in the heart or major vessels of the mediastinum (the “mediastinal blood pool”) and to an ROI placed over normal liver.

Depending on the uptake, a score between 1-5 will be assigned as follows:

Score	Definition
1	No uptake above background
2	Uptake above background, but below mediastinal blood pool
3	Uptake > mediastinal blood pool, but \leq uptake in liver
4	Uptake moderately higher than liver
5	Uptake markedly higher than liver (SUVmax $>2 \times$ normal liver) OR (after treatment has started) New FDG-positive lymphoma lesions

FDG = fluorodeoxyglucose; SUVmax = maximum standardized uptake value.

After screening, in addition to the 5-point scale score the assessment of the FDG-PET also involves an assessment of the overall uptake (a combination of extent and intensity) by tissue consistent with lymphoma, and comparison of this uptake to the baseline and to the scan on which the overall uptake was lowest (nadir).

Metabolic response determination

Metabolic response categories are defined as follows:

Metabolic Response	Definition
Complete metabolic response (CMR)	A score of 1, 2, or 3
Partial metabolic response (PMR)	A score of 4 or 5 (without new lesions), AND Overall uptake decreased compared with baseline
Stable metabolic disease (SMD)	A score of 4 or 5 (without new lesions), AND Overall uptake unchanged compared with baseline and nadir
Progressive metabolic disease (PMD)	A score of 4 or 5 with overall uptake increased compared with nadir, OR with new FDG-positive lesions consistent with lymphoma

In Waldeyer's ring or extranodal sites with high physiologic uptake or with activation within spleen or marrow (eg, with chemotherapy or myeloid colony-stimulating factors), uptake may be greater than normal mediastinum and/or liver. In this circumstance, CMR may be inferred if uptake at sites of initial involvement is no greater than surrounding normal tissue, even if the tissue has high physiologic uptake.

Clinical Data

Bone marrow assessment

To allow an overall response of CR, the bone marrow must be clear of lymphoma (negative for lymphoma).

Lugano allows assessment of bone marrow based on FDG-PET, if the lymphoma type is FDG-avid. Bone marrow on FDG-PET may be normal, may show diffuse uptake (clinical judgment is required because this is also compatible with reactive changes due to chemotherapy or colony-stimulating factors), or may show focal increased uptake that is strongly indicative of lymphoma.

A negative PET allows the bone marrow to be declared negative, even without biopsy, and would support a CR overall (diffuse uptake compatible with reactive changes from chemotherapy or growth factor use can fall into this category). A PR may occur with residual uptake higher than uptake in normal marrow but reduced compared with baseline. If there are persistent focal changes in the marrow in the context of a nodal response, consideration should be given to further evaluation with MRI or biopsy or an interval scan.

Bone marrow aspirate or biopsy is required only as clinically indicated, or if FDG-PET evaluation of bone marrow is judged inconclusive. For lymphoma that is shown at baseline to be non-FDG-avid, aspiration or biopsy is required to declare marrow to be negative. If bone marrow biopsy is performed and shows lymphoma, the bone marrow is considered positive, regardless of the results of the PET.

Physical examination findings

On rare occasions, lesions may be present on physical examination that are not seen on imaging at all. An example might be lymphadenopathy in the popliteal fossa, when the “whole body” imaging includes only anatomy to the midfemur. Such lesions should be documented as nontarget lesions in study forms. They can contribute to progression if new lesions appear this way, and if any were present at baseline, they must disappear for an overall response of CR.

Other clinical data

Information on the use of hematopoietic growth factors and other medications can affect the response assessment as described above.

At certain protocol-specified time points, additional tissue biopsies may be collected and incorporated into the response assessment.

Overall Response

Overall response at each timepoint is determined by combining the anatomic response, metabolic response, and clinical data.

When both CT and FDG-PET are available, the overall response is driven primarily by the metabolic response. When only one imaging modality is available at a given timepoint, that modality is the main determinant of overall response.

Metabolic Response	Anatomic Response	Bone Marrow	Physical Examination	Overall Response
CMR	CR, PR, or SD	Negative	No lesions	CR
PMR	CR, PR, or SD	Any	No new lesions	PR
SMD	CR, PR, or SD	Any	No new lesions	SD
PMD	Any	Any	Any	PD
Any	PD	Any	Any	PD

CMR = complete metabolic response; CR = complete response; PD = progressive disease; PMD = progressive metabolic disease; PMR = partial metabolic response; PR = partial response; SD = stable disease; SMD = stable metabolic disease.

During determination of overall response, if no FDG-PET was performed at the timepoint in question, the results of a preceding PET may be “carried forward”, unless there has been worsening of disease on the CT. For example, if a postbaseline assessment shows a CMR on the PET, and PR on the CT, the overall response is CR. If the next timepoint shows continued PR on the CT, but there is no PET available, the overall response for that visit is still CR.

If there is PR based on either anatomic or metabolic imaging, but a biopsy demonstrates that the tissue in question is not malignant, the response can be upgraded to a CR.

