- a) Have histologically confirmed diagnosis of B-cell lymphoma other than cHL, PMBCL, DLBCL (as described in inclusion criterion 4a), or FL, according to the WHO classification of neoplasms of the hematopoietic and lymphoid tissues [Swerdlow, S. H., et al 2016]. Examples include transformed indolent lymphoma, classical MCL, MZL (both nodal and extranodal), splenic MZL, lymphogranulomatosis, intravascular large B-cell lymphoma, T-cell/histiocyte-rich large cell lymphoma, high-grade B-cell lymphoma (with MYC, BCL2, and/or BCL6 rearrangements), DLBCL with chronic inflammation, B-cell lymphoma unclassifiable, EBV+ DLBCL-NOS and ALK+ large B-cell lymphoma, or small lymphocytic lymphoma. For MCL, documentation of either over-expression of cyclin D1 or presence of t(11;14) is required.
- b) Participants with MCL must have received prior Bruton's tyrosine kinase inhibitor therapy.
- c) Participants must have progressed after at least 2 lines of previous therapy. Participants must have received and failed, been intolerant to, or determined by their treating physician to be a poor candidate or ineligible for a PI3K inhibitor per local (institution) guidelines. Participants who are ineligible for standard treatment or who have withdrawn from standard treatment due to unacceptable toxicity warranting discontinuation of that treatment and precluding retreatment with the same agent before progression of disease will also be eligible. Participants with a indolent lymphoma are required to meet criteria for systemic therapy.
Note: A planned treatment approach of induction therapy followed by auto-SCT, followed by maintenance, is considered 1 line of therapy.
- d) Participants must have exhausted or be ineligible for or intolerant to all standard of care treatment options for their disease per investigator's judgment before enrollment.

7. Cohorts A, B, C, D, and F (non-FDG-avid lymphoma participants):

- a) Have measurable disease, defined as at least 1 lesion that can be accurately measured in at least 2 dimensions with spiral CT scan. Minimum measurement must be >15 mm in the longest diameter or >10 mm in the short axis.

Note: If a target lesion is selected for an excisional screening biopsy, the inclusion criterion for measurable disease must still be met after such biopsy.

- b) Be able to provide newly obtained bone marrow biopsy material for tumor response assessment by local investigator sites.

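### The new-lesion rule in Appendix 8 is not limited to FDG-avid lymphoma, so in non-avid disease progression shown only by a new PET-negative lesion goes unrecorded when a PET is done

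*Combined protocol and SAP*

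**What the plan says.** Inclusion criterion 7 (Section 5.1) sets requirements for "Cohorts A, B, C, D, and F (non-FDG-avid lymphoma participants", so non-avid disease is expected in every lymphoma cohort.

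Section 10.8.1 uses PET positivity in two places that matter here:

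- **Baseline measurability:** "In lymphomas that are FDG-avid, a lesion must be PET-positive (show FDG uptake greater than the surrounding tissue) to be measurable". The condition is limited to avid disease.
- **New lesions after baseline:** "New lesions must be consistent with lymphoma rather than another etiology (eg, infection, inflammation) and must be PET-positive, if PET is available". There is no such limit. The next sentence covers visits without PET: "New lesions will be treated as PET-positive when PET is not available to confirm avidity".

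On the PET schedule, the Metabolic Response text says: "If lesions are not FDG-avid at baseline, PET is not required at follow-up timepoints unless clinically indicated".

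The CT column of the progressive disease table sets no PET condition for new lesions. It lists a new node above 1.5 cm in longest diameter, and also "A new extranodal site of any size, as long as its presence is unequivocal and attributable to lymphoma". The new-lesion text itself, just before the PET sentence, defines a new node by the same size threshold.

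**The concern.** In lymphoma that does not take up FDG, a negative PET says little about whether a new mass is lymphoma. The appendix recognises this elsewhere. It limits the measurability rule to avid disease, allows PET assessment of marrow only in avid lymphoma types, and asks for aspiration or biopsy to call marrow negative in disease that is non-avid at baseline. The new-lesion rule lacks the same limit.

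Whether a new lesion counts as progression can then depend on whether a PET, optional in these participants, was done at that visit. Suspected progression could itself be a reason to order one. The error runs one way, towards late or missed progression. It bears on DOR and, in one situation, on DCR, both secondary endpoints assessed by the investigator.

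**Working it through.** No numerical figure in the plan bears on this point, so the check is a trace through the rules of Section 10.8.1.

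**Case.** A participant whose lymphoma is not FDG-avid at baseline has a new node on CT. It was previously normal in size, is now above 1.5 cm in longest diameter and is consistent with lymphoma. No other progression criterion is met.

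1. **No PET at the visit.** The node is treated as PET-positive and recorded as new. The anatomic response table gives PD for any new lesion, and the overall response table gives PD for any anatomic PD. Result: PD.
2. **PET done, node PET-negative.** The node fails the PET condition and cannot be recorded as new, so the anatomic response is not PD by this route. The overall response then follows mainly from the metabolic category. Result: not PD.
3. **Same visit as case 2, read from the CT column of the PD table.** The node meets the size criterion and no PET condition appears. Result: PD.

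Cases 1 and 2 give opposite answers to the same CT finding. Cases 2 and 3 give opposite answers at the same visit.

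**What happens to the unrecorded node.** Target and nontarget lesions are designated at baseline and the designations are fixed. The node belongs to neither group, so its later growth does not trigger the target or nontarget routes. Through that node alone, PD waits for a visit without PET, or for FDG uptake to appear.

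**Routes that stay open at a visit with PET.**

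- Target growth: "Target lesion progression is based on the progression of any single lesion (not a change in the SPD"), judged by size with no PET condition.
- Unequivocal nontarget progression.
- Spleen enlargement meeting the progression criteria.
- Extranodal lesions that resolved and then reappear; these act like new lesions but are not labelled new.
- New or recurrent marrow involvement.
- New lesions on physical examination, which can contribute to progression.

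Some nonmeasurable new lesions, such as CNS lesions and infiltrative masses, need no verification. The text does not say whether that also waives the PET condition.

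**Effect on the endpoints (Section 9.4.1).**

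- DOR ends at progression or death, so a late or missed PD can lengthen it.
- DCR counts any responder, or stable disease lasting at least 12 weeks before progression. A late PD changes it only for a non-responder whose stable disease is wrongly carried past 12 weeks.
- A response already recorded stays in the ORR when a later PD is missed.

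**The case against.** The strongest reply is that the intent can be recovered. The rule speaks of PET confirming avidity, which makes sense only where avidity is expected, and the appendix treats non-avid disease separately elsewhere. Follow-up PET is optional in these participants, and without it the rule gives the expected result. The response tables are introduced as summaries, with implementation left to the text that follows, so the PD table and the new-lesion text are not two rules of equal standing.

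Much of this stands. It narrows the exposure and weakens the conflict with the table. It does not supply the missing limit. If the detailed text governs, the literal rule is the one that gives the wrong answer in case 2.

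A reader might infer that real progression in non-avid disease cannot be recorded at all at a visit with PET. The documents do not support that, since the routes listed above remain and any anatomic PD gives overall PD whatever the PET shows.

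A reader might also infer that treatment would continue without a recorded progression. That is not shown either. Section 7.1 allows discontinuation at the investigator's discretion on several grounds, and the disease-progression section it refers to (8.2.4) is redacted.

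The schedule of activities and Section 8.2 are redacted, and the Site Imaging Manual is a separate document. Any of them might address PET in non-avid disease; this cannot be checked.

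**Conclusion.** The point holds in a narrow form. The PET condition for new lesions lacks the FDG-avid limit that the baseline rule carries, and it is at odds with the CT column of the PD table and with the size-based definition in the same new-lesion text. In lymphoma that is not FDG-avid at baseline, progression shown only by a new PET-negative lesion would not be recorded at a visit where a PET is done.

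The direction is clear: PD late or missed, DOR longer in affected responders, and DCR higher in the one situation described. The size cannot be estimated. The documents do not give the number of non-avid participants, how often they have a follow-up PET, or the share of progressions shown only by a new PET-negative lesion. All three conditions must coincide, so the effect is probably small.

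Three tempting figures should not be attached to it:

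- A count of affected participants per cohort would rest entirely on assumed inputs.
- A 12-week delay would borrow the Efficacy Follow-up interval in Section 8.11.4.2; the on-treatment schedule is redacted.
- A shift of 1/30 = 3.3 percentage points in a cohort rate does not follow from a late PD, because DOR is not a rate and DCR moves only in the situation described.

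The endpoints are secondary and descriptive, no hypothesis is tested, and the primary endpoint is safety. This is a low-severity wording correction.

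**What to change.** Amend the new-lesion text in Section 10.8.1 in two steps.

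- Limit the PET condition, for example: *In lymphoma that is FDG-avid at baseline, a new lesion must also be PET-positive if a PET is available.*
- Add a sentence for other lymphoma, for example: *In lymphoma that is not FDG-avid at baseline, new lesions are judged on the CT size and etiology criteria of this section, whether or not a PET was done.*

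The first step reuses a limit already present in the measurability rule, and the second points to criteria already in the appendix. Together they bring the new-lesion text into line with the CT column of the PD table for non-avid disease. The cost is two sentences, with no new data, imaging or procedures. The sponsor should also check that the redacted imaging sections and the Site Imaging Manual agree with the revised wording.
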